## 5. Methods

All CCRMC patients who meet the inclusion criteria will receive the same basic email or SMS message, inviting them to participate in the APT Webstudy. Eligible CCRMC patients will be allocated 1:1:1 to 3 study arms. The first arm, the messaging only arm, will just receive the invite message. The 2nd arm will receive, along with the invite, the offer of a \$25 gift card for completing enrollment into the APT Webstudy. The 3rd arm will receive, along with the invite, an offer of entry into a \$2500 prize drawing for completing enrollment into the APT Webstudy. The prize opportunity will be designed to allow participants to have a 1 in 100 chance of winning a \$2500 prize, thus the prize opportunity has the same expected value per enrollee as the certain \$25 incentive. Registration for and enrollment in the APT Webstudy includes web-based capture of demographic, medical, lifestyle and risk factors, as well as longitudinal web-based cognitive testing and symptom questionnaires. One cognitive assessment, the Cogstate Brief Battery, is a cognitive performance test; the other, the Cognitive Function Index (CFI), is a series of 15 questions probing subjective concerns related to cognitive performance. Participants will qualify as enrolled in the APT Webstudy if they complete the registration process as well as at least one of the two cognitive assessments. None of the data captured in the APT Webstudy data will be shared with the research team.

Two messages will be sent out to all eligible CCRMC patients, an initial invitation and a follow-up reminder will be sent approximately 2-weeks later. Invitations will be made via SMS or e-mail, depending on members' previously indicated mode of communication with the health system.

The intervention will be implemented by our collaborating partner, Contra Costa Health Services (CCHS), which runs Contra Costa Regional Medical Center (CCRMC) The trial team will track returned/invalid email or phone numbers as well as requests to opt out of communications at the participant level.

[figure not shown]

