## **b. Sample size determination**

Data used in the power analysis are based on members ages 50 and over without MCI/Dementia currently included in the CCHS database. We power the study for the primary endpoint – enrollment rates. We based our power calculations on a two-sided chi-square test for detecting a difference between two proportions, assuming a type I error rate of 2.5% (to account for the two hypotheses of interest). With a sample size of 16,000 members in each treatment arm (48,000 overall), and assuming an enrollment rate of 2% in the active control arm, we have 90% power to detect an absolute difference of 0.59% or higher (an enrollment rate of 2.59% or higher) in either of the two financial incentive groups.

We also plan to conduct sub-group analyses, with a particular focus on racial and ethnic minorities. With sample sizes of 2100, 3600, 2940, and 5380 per arm in the Black, Asian, Latino(a) and White sub-groups, and assuming the same 2% enrollment rate in the active control arm, we have 90% power to detect an enrollment rate of 1.8%, 1.34%, 1.5% and 1.07% respectively in either of the two financial incentive arms. The sample size also provides adequate power to detect meaningful differences in other pre-specified populations of interest (based on primary language (English/Spanish), and age group (50-64, 65-74, 75 and over).

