### **c. Statistical Analysis**

The primary analysis will be based on the intention-to-treat (ITT) population of all messaged patients who are empaneled at Contra Costa Regional Medical Center (CCRMC), who are ages 50 and older and have no prior documentation of dementia.

Participant demographics and characteristics at time of messaging will be summarized for each intervention arm, using frequencies and percentages for categorical variables, and using mean, standard deviation, and quartiles for continuous variables. Comparisons across the three intervention groups will be done using a Chi-square test for categorical variables and an analysis of variance (ANOVA) test for continuous variables with Fisher's Exact Test or Dunnett's post-hoc tests, for categorical and continuous data respectively, to compare each active intervention arm against the control arm.

Our primary outcome is the enrollment status at 2-weeks. A multivariable logistic regression analysis will be performed to study the association between enrollment status and intervention arms (financial incentive arms vs active control arm) adjusting for age group (50-64, 65 and over), race and ethnic status (Latino/Hispanic, non-Hispanic White, non-Hispanic Black, non-Hispanic Asian, Other) and message modality (email or text). Separate analyses will be conducted for each financial incentive intervention arm against the active control arm.

All results will be reported as point estimates (e.g., percentage difference between groups) and interval estimates (two-sided 95% confidence intervals). All hypothesis tests to test group differences between each of the active intervention arms and the active control arm will be conducted at a two-sided alpha level of 0.025.

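### Optional improvement: a Holm step-down for the two primary incentive-versus-control tests would keep the 5% family-wise bound and add power for the second contrast, at no extra sample size

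*Protocol*

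**What the plan says.** Protocol section 5b (Sample size determination) rests its power on a "two-sided chi-square test for detecting a difference between two proportions". The level reflects the number of comparisons, since the section works "assuming a type I error rate of 2.5% (to account for the two hypotheses of interest"). The planned size reads "With a sample size of 16,000 members in each treatment arm (48,000 overall"). The control rate is fixed by "assuming an enrollment rate of 2% in the active control arm". The resulting claim, made for each incentive group, is "we have 90% power to detect an absolute difference of 0.59% or higher (an enrollment rate of 2.59% or higher").

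Protocol section 5c (Statistical Analysis) follows the same scheme: "Separate analyses will be conducted for each financial incentive intervention arm against the active control arm", and tests of each incentive arm against control "will be conducted at a two-sided alpha level of 0.025". The level does not change once one of the two tests has been rejected. Results are to be reported with two-sided 95% confidence intervals. Later in 5c, secondary outcomes are also tested at 0.025, and subgroup analyses use methods analogous to the overall analysis.

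**The concern.** Holding both tests at 0.025 whatever the first one shows is plain Bonferroni. Once one null hypothesis has been rejected, only one remains, and testing that one at 0.05 still keeps the family-wise error at or below 0.05. The fixed level leaves this unused.

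What is at stake is the second contrast. The primary objective and the first hypothesis name both kinds of incentive. If both work, the fixed level makes it somewhat more likely that only one is declared effective. Extra power cannot easily come from extra members, because the protocol plans to message all eligible patients.

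**Working it through.** **Inputs.** All from the protocol: 16,000 per arm, 1:1:1 allocation, control rate 0.02, incentive rate 0.0259, two contrasts sharing one control arm, two-sided 0.025 per contrast, chi-square test. Rates other than 2.00% and 2.59% are assumptions, used only to show a range.

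**Step 1: reproduce the stated power.** With the pooled rate p̄ = (0.02 + 0.0259)/2 = 0.02295:

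- SE under the null: s0 = √(2 × 0.02295 × 0.97705 / 16,000) = 0.0016742
- SE under the alternative: s1 = √((0.02 × 0.98 + 0.0259 × 0.9741) / 16,000) = 0.0016739
- Critical value for two-sided 0.025: 2.2414
- Power = Φ((0.0059 − 2.2414 × 0.0016742) / 0.0016739) = Φ(1.283) = 90.02%

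The sample size needed for 90% power is 15,988 per arm, so the protocol's figure reproduces.

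**Step 2: write Holm in the same terms.** Holm tests the smaller p-value at 0.025. If it is rejected, the other is tested at 0.05. Let B be the probability that both contrasts pass at 0.025, and M the probability that a given contrast passes at 0.025 and the other at 0.05. Then:

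- Power for both: Bonferroni B; Holm 2M − B
- Power per contrast: Bonferroni 90.02%; Holm 90.02% + (M − B)
- Power for at least one: identical, because both rules start by testing the smaller p-value at 0.025

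The shared control arm gives a correlation of 0.0196 / (0.0196 + 0.02523) = 0.437 under fixed variances. The bivariate normal then gives B = 0.8291 and M = 0.8606. Hence Holm for both = 2 × 0.8606 − 0.8291 = 0.892, and Holm per contrast = 0.9002 + 0.0315 = 0.932.

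**Step 3: simulate.** 2,000,000 three-arm trials per scenario, binomial arms of 16,000, shared control at 2.00%, pooled z-tests. The simulated correlation is about 0.50. Putting 0.50 into the step 2 formulas gives 83.3% and 89.4% for both effects, close to the simulated values.

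| True rates in the two incentive arms | Measure | Fixed 0.025 | Holm |
|---|---|---|---|
| 2.59%, 2.59% | power per contrast | 90.1% | 93.2% |
| 2.59%, 2.59% | power for both | 83.4% | 89.5% |
| 2.59%, 2.59% | power for at least one | 96.9% | 96.9% |
| 2.59%, 2.50% | power, second arm | 78.1% | 84.3% |
| 2.50%, 2.50% | power for both | 66.2% | 75.7% |
| 2.59%, 2.00% | power, effective arm | 90.1% | 90.3% |
| 2.59%, 2.00% | false rejection, null arm | 2.5% | 4.5% |
| 3.00%, 2.00% | false rejection, null arm | 2.5% | 5.0% |
| 2.00%, 2.00% | any false rejection | 4.6% | 4.6% |

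**Step 4: express the gain in members.** At the design alternative, the fixed-level rule would need about 17,900 per arm to equal Holm's power per contrast, or about 18,500 per arm to equal its power for both. Over three arms that is 3 × 1,900 = 5,700 or 3 × 2,500 = 7,500 more members.

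**The case against.** The strongest reply is that this is a choice between two valid procedures. Design and analysis agree on 0.025, and the power target is met. That target is power for either incentive group; the protocol sets no target for showing both. All of this stands, which is why the point is a suggestion. It is still more than a matter of taste, because Holm rejects whenever the fixed rule does and sometimes when it does not.

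Three stronger readings are tempting and are not supported:

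- *The trial is underpowered or the 0.025 rule is wrong.* Step 1 shows otherwise.
- *Holm improves the chance of success whatever the truth.* Power for at least one rejection is unchanged, and with only one working incentive the gain is about 0.2 points.
- *The family-wise error is the same throughout.* Only the 5% bound and the rate with both nulls true are the same. When one arm works and the other does not, Holm rejects the null arm more often, though never above 5%.

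A second reply concerns intervals. Under the fixed rule, moving from 95% to 97.5% intervals would align tests and intervals exactly, whereas Holm has no simple matching simultaneous intervals. That cost is real but small: section 5c already pairs 95% intervals with 0.025 tests, so the plan as written has no such alignment to lose.

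A third reply is that the edit reaches beyond one sentence, since the secondary-outcome and subgroup wording leans on the primary rule. That is right, and the fix covers it.

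**Conclusion.** This is a cheap improvement, not an error. The fixed 0.025 level is valid and gives the stated 90% power. Under the same 5% family-wise bound, Holm adds about 3 points of power per contrast and 6 points for showing both effects, if both incentives reach 2.59% against 2.00%. The chance of missing at least one of two real effects then falls from 16.6% (100 − 83.4) to 10.5% (100 − 89.5).

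The benefit depends on both incentives working. The figures assume 16,000 per arm and the chi-square test of section 5b, not the covariate-adjusted logistic model of 5c. Holm's error bound itself does not depend on the correlation between the two tests. The SAP is not at hand, so this concerns the rule as the protocol states it.

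**What to change.** Before any unblinded analysis:

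1. In section 5c, for the primary endpoint in the overall population only, replace the fixed level with: *The two incentive-versus-control tests use the Holm procedure at a two-sided family-wise level of 0.05 (smaller p-value at 0.025; if rejected, the other at 0.05).*
2. Leave the sample size in 5b as it is, and describe its 0.025 basis as conservative.
3. In the secondary-outcome and subgroup text of 5c, state that the 0.025 level is retained there.
4. Label the reported 95% intervals as unadjusted for multiplicity. If 97.5% intervals are added, note that they may include no effect for an arm rejected only at the second step; p = 0.03 for the second contrast is an example.

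The cost is a few sentences, with no new data and no change in sample size. What is given up is the option of exact agreement between tests and intervals, together with a higher false-rejection rate, up to 5%, for an ineffective arm when the other arm works.

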### **d. Data Protection, Storage and Sharing**

Contra Costa Health Services (CCHS), which runs Contra Costa Regional Medical Center, will conduct an initial screen of their EMR and provide the research team with a de-identified dataset with basic

demographics (age, sex, race/ethnicity and primary language) of patients ages 50 and above without a dementia diagnosis. That dataset will be used to randomize patients to study arms. A partial waiver of HIPAA authorization will be requested from IRB for the purposes of identifying qualified individuals. Individuals recruited to the APT study will be consented within the APT Webstudy system.

Data shared for randomization will be de-identified. Messaging will be performed by the health system. Deidentified data will be transferred between Contra Costa Health System (CCHS) and USC for the purposes of randomization. USC will also provide CCHS with the unique deidentified codes for members who enroll in the APT Webstudy. Only CCHS holds the key to identify these members. Where applicable the health system will make incentive payments to these members. All data transfers between CCHS and USC will rely on the USC secure file sharing platform, Box, which encrypts data during transfer and at rest. USC and CCHS will execute appropriate data use agreement(s) before transferring any data.

#### Measures Taken to Ensure Confidentiality of Data Shared per the AHA Data Sharing Policies

It is AHA policy that the results and accomplishments of the activities that it funds should be made available to the public (see <https://professional.heart.org/en/research-programs/aha-research-policies-and-awardee-hub/open-science-policy-statements-for-aha-funded-research>). The PIs will ensure all mechanisms used to share data will include proper plans and safeguards for the protection of privacy, confidentiality, and security for data dissemination and reuse (e.g., all data will be thoroughly de-identified and will not be traceable to a specific study participant). Plans for archiving and long-term preservation of the data will be implemented, as appropriate.

Participant privacy and confidentiality for the APT Webstudy will be protected as described in USC IRB #HS-17-00746. No added risks to privacy or confidentiality are anticipated. All user and study data are stored and maintained on servers hosted on Amazon Web Services under an Enterprise Agreement and a Business Associate Agreement with USC which stipulates rights and responsibilities between both parties. All data is encrypted in transit and at rest.

Data collected for this study will be analyzed and stored at the University of Southern California (USC). APT Webstudy enrollment data will be maintained at USC's Alzheimer's Therapeutic Research Institute (ATRI) and data usage will be guided by the APT Webstudy data sharing plan.

